### 7.3 Early discontinuation of study participation

Patients who experience protocol-defined progression will have attained the primary study outcome and will undergo treatment either with radical prostatectomy or whole gland image guided radiotherapy of the prostate at the University of Miami. Their histopathology (for surgery patients) and rates of biochemical recurrence will be followed and compared to historical series for comparison with cohorts not undergoing MRI guided selection for surveillance versus immediate treatment. However, those who refuse the recommendation for treatment will continue to be followed per active surveillance standard of care guidelines. Furthermore, those who seek treatment outside UM will be contacted for information on histopathology (for those undergoing surgery) and rates of biochemical recurrence. Patient refusal of the recommendation for treatment or further follow-up beyond progression will not be a protocol deviation. Patients who are without progression upon completion of the third annual biopsy will be censored without progression.

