The procedure will be performed by an urologist in the Department of Urology [name] at the University of Miami. For patients with MRI visible lesions, an MRI-US fusion biopsy will be performed in addition to the standard template (above). MRI-US fusion biopsies will be performed preferably using the Uro-Nav system from Invivo, Philips; although, the Artemis system is available in the department of urology and may be used.

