### **7.6 Biopsy Tissue Handling**

Immediately following each biopsy core, the tissues will be fixed in 10% formalin per routine. The formalin fixed tissues will be delivered to the Department of Pathology for paraffin embedding and sectioning.

The biopsies are to be placed in the tissue processor and processed routinely, and embedded in paraffin. Biopsies will be reviewed by a pathologist and the results (Gleason scoring and percent of tumor tissue) recorded in the patient's record per routine. The remainder of the block will be stored per institutional policy in the Department of Pathology and requests for the biomarker analyses made at a time batched staining is possible (after a number of cases have been accrued).

When the tissue is sectioned for biomarker analyses, the slides will be labeled with a research ID number and will not contain patient information. Biomarker data will be entered into the Active Surveillance Database, which links the patient Medical Record number to a participant's Research ID number and in which data on each patient related to biopsies and treatments will be recorded. De-identified data will be sent to Genome Dx for gene expression profiling as described below.

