## 10.1 Primary Study Endpoints

### 10.1.1 Progression

The main study endpoint will be the 24-month cumulative progression rate. In the context of this trial, progression refers to a repeat surveillance biopsy indicating any one of the following: (i) more than 4 positive cores involving any grade of cancer, (ii) three or more cores with Gleason 3+4 cancer, (iii) any single core with Gleason 4+3 cancer or higher, (iv) a Gleason 3+3 at diagnosis that is upgraded to Gleason 3+4 or (v) undergoing treatment, regardless of histological progression. Although many existing active surveillance protocols incorporate volume of cancer in their definition of progression, these are based on random biopsy of the prostate. Critical volumes of cancer based on targeted biopsy have not been defined and will be explored in this analysis.

- Progression rate will be estimated for each scheduled surveillance biopsy as the proportion of study patients without prior progression for whom the biopsy indicates progression.
- Cumulative progression rate will be estimated for each of the four planned biopsies as the proportion of patients with progression among those having had all planned biopsies to date, or a previous biopsy indicating progression.

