### 10.1.2 Histological progression

In the context of this trial, histological progression refers to a surveillance biopsy that indicates any one of the following: (i) more than 4 positive cores involving any grade of cancer, (ii) three or more cores with Gleason 3+4 cancer, (iii) a Gleason 3+3 at diagnosis that is upgrade to Gleason 3+4, or (iv) any single core with Gleason 4+3 cancer or higher.

- Histological progression rate will be estimated for each scheduled biopsy as the proportion of study patients without prior GS progression for whom the biopsy indicates GS progression.
- Cumulative histological progression rate will be estimated for each scheduled biopsy as the proportion of patients with histological progression among those having had all planned biopsies to date, or a previous biopsy indicating Gleason score progression.

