#### 10.2.3 Area under ROC curves as predictive measure and incremental prediction improvement for progression

Patients will be categorized at baseline by NCCN risk class ranging from very low risk to intermediate risk and into those who progressed while on the trial and those who did not. Logistic regression will be used to model the association between NCCN risk class and progression using AUC for ROC curves. The incremental benefit of mpMRI, genomic testing and molecular markers compared to NCCN risk alone will be evaluated by comparing AUC using a likelihood ratio test. MRI will be categorized from 1-5 using PIRADS, while genomic test scores and molecular markers can be used as continuous scores or categorized into levels of risk (low/ intermediate/high).

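### The marker analysis in Section 10.2.3 appears to count treatment without histological progression as progression, so its AUC and likelihood ratio test mix disease with treatment behaviour, and the bias can go either way

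*Combined protocol and SAP*

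**What the plan says.** Section 10.1.1 is the only definition headed Progression. It lists four biopsy criteria and adds a fifth, "undergoing treatment, regardless of histological progression". Section 10.2.3, which serves secondary objective 3, divides men "into those who progressed while on the trial and those who did not". It does not say that only the biopsy criteria count. For the markers, "MRI will be categorized from 1-5 using PIRADS", and the gain over NCCN class is to be "evaluated by comparing AUC using a likelihood ratio test", within logistic regression.

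An outcome without the treatment criterion already exists. Section 10.1.2 begins: "In the context of this trial, histological progression refers to a surveillance biopsy that indicates any one of the following", and its list contains only biopsy findings. Section 10.5 plans it for time-specific and cumulative rates and does not name it for the marker analysis. No marker analysis without the fifth criterion is planned.

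No masking of the MRI is described. Under Section 7.5, "For patients with MRI visible lesions, an MRI-US fusion biopsy will be performed in addition to the standard template". Section 7.3 sets the trial's patients against historical series for "comparison with cohorts not undergoing MRI guided selection for surveillance versus immediate treatment", so MRI is part of how men are selected for treatment.

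Two other places describe progression differently. The opening of Section 10 says the primary endpoint rests on biopsy criteria, which does not fit the fifth criterion. Section 3.1 glosses progression as conversion to treatment.

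**The concern.** A man whose biopsy meets none of the four criteria may still choose treatment. If a suspicious MRI contributed to that choice, Section 10.1.1 records an event, and Section 10.2.3 credits the MRI with predicting it. If the choice had nothing to do with the MRI, the event is noise and hides some of whatever predictive value PI-RADS has for disease. In both cases the AUC answers a mixed question: who has worse disease, and who opts for treatment.

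At stake is secondary objective 3, the added value of mpMRI, genomic tests and molecular markers over NCCN class. The result could overstate or understate what MRI says about disease. The serial marker analysis in Section 10.3.4 relates markers to progression on trial and has the same exposure. Section 10.3.3 uses progression on the baseline biopsy and is less exposed.

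**Working it through.** **The plan's own figure.** The documents give no operating characteristic for the marker analysis. The only stated power, 97.3% in Section 10.4 (150 patients, 12.5% against 25%, two-sided 5% binomial test), reproduces: the exact test rejects at 28 or more of 150, with upper-tail error 0.0193 and power 97.34%. It is not in question here.

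**Inputs.** The 25% progression rate is the alternative in Section 10.4, used here as the rate of histological progression (an assumption). The share of men with PI-RADS 4-5 (40%, range 30-50%) and the share treated without histological progression (2-5%) are assumptions; the documents give neither.

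**Formula.** For a marker split at PI-RADS 4-5, AUC = 0.5 + (sensitivity - false-positive rate)/2.

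**Case A: PI-RADS unrelated to histology, all treatment-only events in PI-RADS 4-5.** Per 100 men, 10 histological events fall in PI-RADS 4-5 and 15 elsewhere. With e treatment-only events, sensitivity = (10 + e)/(25 + e) and false-positive rate = (30 - e)/(75 - e).

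| e | Sensitivity | False-positive rate | AUC |
|---|---|---|---|
| 2 | 12/27 = 0.444 | 28/73 = 0.384 | 0.530 |
| 3 | 13/28 = 0.464 | 27/72 = 0.375 | 0.545 |
| 5 | 15/30 = 0.500 | 25/70 = 0.357 | 0.571 |

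With PI-RADS 4-5 in 30-50% of men, the range is 0.525-0.583. The true histological AUC is 0.50 throughout.

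**Case B: weaker link.** Treatment-only is now twice as likely in PI-RADS 4-5. Non-progressors number 30 in PI-RADS 4-5 and 45 elsewhere, so the PI-RADS 4-5 share of treatment-only events is 60/(60 + 45) = 0.571. At e = 5 that is 2.86 events: sensitivity 12.86/30 = 0.429, false-positive rate 27.14/70 = 0.388, AUC 0.520. At e = 2 it is 1.14 events: 11.14/27 = 0.413, 28.86/73 = 0.395, AUC 0.509.

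**Case C: informative PI-RADS, treatment unrelated to MRI.** Put 70% of the 25 histological events in PI-RADS 4-5: 17.5 there, 7.5 elsewhere. Sensitivity is 0.70, false-positive rate 22.5/75 = 0.30, AUC 0.70. Add 5 treatment-only events at the same rate in all non-progressors: 1.5 in PI-RADS 4-5, 3.5 elsewhere. Sensitivity becomes 19/30 = 0.633, false-positive rate 21/70 = 0.30, AUC 0.667. The bias is downward.

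**Where the direction turns.** In Case C, let a fraction f of the 5 treatment-only events fall in PI-RADS 4-5. The AUC stays at 0.70 when (17.5 + 5f)/30 - (22.5 - 5f)/70 = 0.40, which gives f = 0.58 (20.4/30 - 19.6/70 = 0.68 - 0.28). Below that it falls; above it rises, to 0.75 at f = 1 (22.5/30 - 17.5/70 = 0.50).

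**Likelihood ratio test.** This was simulated with 150 men, PI-RADS 2 or less/3/4/5 in 40/25/25/10%, 25% composite progression, an NCCN class unrelated to outcome, PI-RADS unrelated to histology, and 1,000 runs per cell (Monte Carlo error about 0.7 points at 5%). If 20% of events are treatment-only (5% of men):

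| Treatment-only events by PI-RADS | Composite AUC | Rejections at nominal 5% |
|---|---|---|
| Unrelated | 0.50 | 6% |
| Twice as likely at 4-5 | 0.52 | 7% |
| 1:2:4:4 across the four groups | 0.54 | 11% |
| Only at 4-5 | 0.59 | 37% |

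No multiplicity adjustment was applied.

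**The case against.** **Materiality.** The documents do not show that treatment without histological progression is common. Section 1.5.1 reports 64 biopsy progressions, 61 of them treated, and no count of men treated without progression. Sections 4, 7.3 and 7.9 tie treatment to protocol-defined progression, and nowhere is MRI alone a treatment trigger. This stands as a limit on size. It does not settle which outcome Section 10.2.3 uses.

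**Choice of target.** Section 3.1 equates progression with conversion to treatment. If the aim is to predict leaving surveillance, treatment is a legitimate event. That is arguable for the composite, and is a reason to keep it as a sensitivity analysis. The opening of Section 10 points the other way, to biopsy criteria. Section 10.2.3 cites no definition by number, so the outcome needs naming on any view.

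**Stronger readings the documents do not support.** A reader might infer that the AUC of MRI is necessarily inflated, or that bias vanishes only when treatment is unrelated to the MRI. Case C refutes both. A reader might also infer that PI-RADS earns all its credit by causing treatment; at most this concerns treatment-only events, and PI-RADS may still predict the histological ones. Nor does the text show that genomic markers could not influence the decision. Section 7.6 has "requests for the biomarker analyses made at a time batched staining is possible (after a number of cases have been accrued", which covers tissue work only and is silent on blood and urine markers. NCCN class is also known to clinicians, so the comparator may be exposed too.

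**Scope of the arithmetic.** Cases A to C give stand-alone AUCs for a dichotomised marker, not the increment over NCCN class. That is correct; only the simulation addresses the added-value test.

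**Conclusion.** The point holds. As written, Section 10.2.3 uses an outcome whose only matching definition includes treatment without histological progression, and MRI may influence that treatment. The AUC and the likelihood ratio test therefore partly measure treatment behaviour.

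The size is unknown because the rate of such treatment is not given. Under the stated assumptions, an uninformative PI-RADS would show a stand-alone AUC of about 0.53-0.57 in the extreme where every treatment-only event has PI-RADS 4-5, and 0.51-0.52 under a 2:1 link. An informative PI-RADS can lose about 0.03 (0.70 to 0.67) when such treatment is unrelated to MRI. The direction depends on how closely treatment-only events track PI-RADS compared with histological events. This affects a secondary objective and one exploratory analysis, and no change to the primary endpoint is needed to correct it.

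**What to change.** - In Sections 10.2.3 and 10.3.4, name histological progression (Section 10.1.2) as the main outcome and report the Section 10.1.1 composite as a sensitivity analysis.
- State how men treated without histological progression are handled. Either use a competing-risk analysis with a time-dependent AUC (Section 10.5 already allows competing-risk methods), or keep logistic regression and show results twice: with these men excluded, and with them counted as non-events. Simple censoring does not fit the logistic model, and it may be informative if treatment follows the MRI.
- Report the number of such men by PI-RADS category, so that readers can judge size and direction.
- Reconcile the opening of Section 10 with the fifth criterion in Section 10.1.1.

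**Cost.** The outcome is already defined and collected. The logistic route needs only SAP wording; the competing-risk route changes the model. Some events leave the main marker analysis: 2/27 = 7% if 2% of men have such treatment against 25% histological progression, and 5/30 = 17% if 5% do. The change does not remove all dependence on MRI, because under Section 7.5 visible lesions receive added targeted cores, which can themselves produce a histological event. State this as a limitation.

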## **10. STATISTICAL CONSIDERATIONS**

This is a single-arm trial with the primary objective of determining the rate of progression over 2 years in men undergoing AS who are managed with multiparametric-

MRI and MRI-US fusion prostate biopsies, as compared to historical controls. The primary study endpoint is the 24-month cumulative progression rate based on biopsy criteria.

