### **10.4 Sample size, accrual rate and study duration**

We plan to accrue approximately 55 patients per year for the first three years of the study; this assumes a 10% dropout rate. The power (97.3%), is based on 150 patients, using a two-sided binomial test at the 5% significance level to detect an increase in the 24-month cumulative progression rate from 12.5%, as expected for AS historically, to 25% for MRI-AS. Enrollment will occur during the first 3.25 years. Enrollment will be completed at < 3.33 years from the enrollment of the last patient.

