## 10.5 Statistical Analysis

Descriptive statistics will be done for patient demographics and baseline disease characteristics. Counts and percentages will be used to summarize the distribution of categorical variables while median, range, mean and standard deviation will be used for continuous variables. Baseline characteristics will include age, race/ethnicity, T-stage, Gleason score, PSA, PSAD and performance status. Continuous scores will be compared using ANOVA and linear regression controlling for common demographic and clinical variables.

For each scheduled surveillance biopsy session, we will tabulate patients and the following status categories: biopsy indicating progression, biopsy negative for progression, biopsy not performed for progression detected on earlier biopsy, biopsy not performed because patient refused, or biopsy not performed because patient dropped out of study.

Time to event endpoints such as progression and BCR will be analyzed by Kaplan-Meier (KM) or competing risk (CR) methods. Where the Kaplan Meier method is used, point estimates and two-sided 95% confidence intervals for rates will be reported for selected times using Greenwood's variance and the log-log transform method. Median survival time, if attained, will also be reported. We will report the progression rate and the cumulative progression rate for each surveillance biopsy. Taking the third scheduled biopsy at the end of 2 years as illustration, the progression rate at 24 months is the proportion of biopsied patients indicating progression among the total number of biopsied patients over the 24 month period. The 24-month cumulative progression rate is the primary endpoint, which will include those who complete the first three biopsies or have progression from the first or second biopsy. The primary endpoint, 24-month cumulative progression rate, will be estimated and reported with corresponding 95% confidence intervals. Groups will be compared by the log rank test. In addition, we will report and plot the cumulative progression rates in each arm for the four scheduled surveillance biopsies. It is expected that the early difference with historical values and those obtained with MRI-guided biopsies will not be sustained; that is, the 36-month cumulative progression rates will be approximately equal. Similar estimation of time-specific and cumulative rates will be done for Histological progression.

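### The primary 24-month rate keeps every man who progresses at biopsy 1 or 2 but drops men without progression who miss biopsy 2 or 3, so random dropout after biopsy 1 can only raise it: a small overstatement, in the direction of the trial's hypothesis

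*Combined protocol and SAP*

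**What the plan says.** Section 10.1.1 defines the cumulative rate as "the proportion of patients with progression among those having had all planned biopsies to date, or a previous biopsy indicating progression". Section 10.5 repeats the rule for the 24-month primary endpoint, "which will include those who complete the first three biopsies or have progression from the first or second biopsy". Section 10.1.2 carries it into the histological endpoint: "the proportion of patients with histological progression among those having had all planned biopsies to date". In this schedule biopsy 1 is the initial protocol biopsy, and biopsies 2 and 3 follow at 12 and 24 months.

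The plan expects losses. Section 10.4 says of its accrual figure that "this assumes a 10% dropout rate", without timing or base. The tabulation in 10.5 has categories for "biopsy not performed because patient refused, or biopsy not performed because patient dropped out of study".

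Two other parts of the plan bear on the point. Section 10.1.1 also specifies a progression rate at each biopsy among men without prior progression. Section 10.5 says "Time to event endpoints such as progression and BCR will be analyzed by Kaplan-Meier (KM) or competing risk (CR) methods", with Greenwood variance and log-log intervals. Neither is assigned to the primary rate. Section 7.3 states censoring only for men who finish the third annual biopsy without progression.

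The status of men treated between biopsies is unclear. Section 10.1.1 lists as a form of progression "undergoing treatment, regardless of histological progression". The opening of section 10 says "The primary study endpoint is the 24-month cumulative progression rate based on biopsy criteria", and the denominators mention only biopsies.

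**The concern.** Entry to the denominator depends on the outcome. Early progressors stay whatever they do later; men still negative stay only if they complete the series. Loss unrelated to disease thus removes non-progressors more often than progressors, and the ratio rises.

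The trial has one arm and its rate is read against a fixed 12.5%, so any upward shift is read as an effect of MRI. The shift grows as progression is found earlier, which is what the first hypothesis in section 2 predicts.

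**Working it through.** **Inputs.** Section 10.4: null 12.5%, alternative 25%, 150 patients, two-sided 5% binomial test, power 97.3%, 10% dropout. Section 1.5.1: historical progression of 7%, 18% and 17% at the first, second and third re-biopsies. Assumptions: random dropout; the timing of loss and of progression, which the plan does not give; an exact test with equal tails.

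**The plan's own figure.** With n = 150 and p = 0.125 the exact test rejects at 28 or more (tail 0.0193) or 10 or fewer (tail 0.0153), so its actual two-sided error is 3.5%. At p = 0.25 the chance of 28 or more is 97.3%. The stated power reproduces.

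**Formula.** Let q1, q2, q3 be the true shares progressing at biopsies 1 to 3, with sum p, and k1, k2, k3 the probabilities of still being in follow-up at each biopsy. The planned ratio has expectation close to P/(P + C), where P = k1q1 + k2q2 + k3q3 and C = k3(1 - p). If all loss precedes biopsy 1, k1 = k2 = k3 and the ratio equals p. If all progression is found at biopsy 3, it also equals p. Otherwise, with loss after biopsy 1, early progressors carry more weight than C and the ratio cannot fall below p.

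**Largest values** (all progression found before the loss):
- 10% of men not yet progressed: 0.125/(0.125 + 0.875 × 0.9) = 13.70% (+1.2); 0.25/(0.25 + 0.75 × 0.9) = 27.03% (+2.0).
- 10% of all enrolled: 0.125/0.9 = 13.89% (+1.4); 0.25/0.9 = 27.78% (+2.8).

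**Between the extremes.** True 12.5%, 10% loss among men not yet progressed:

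| Timing of progression | All loss before biopsy 2 | Even over last two intervals | All loss before biopsy 3 |
|---|---|---|---|
| Section 1.5.1 rates, scaled to 12.5% | 12.71% | 12.97% | 13.24% |
| Equal risk per biopsy | 12.92% | 13.12% | 13.32% |
| Section 1.5.1 rates in reverse order | 13.01% | 13.26% | 13.51% |
| All at biopsy 1 | 13.70% | 13.70% | 13.70% |

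Worked cell, first row, last column: scaling the three conditional risks by about 0.31 gives shares 0.0217, 0.0546 and 0.0487. Then P = 0.0217 + 0.0546 + 0.9 × 0.0487 = 0.1201, C = 0.875 × 0.9 = 0.7875, and P/(P + C) = 13.24%.

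The scaling is an assumption. Unscaled, and read as conditional rates, the figures accumulate to 1 - 0.93 × 0.82 × 0.83 = 36.7% over three biopsies. The reverse order is also assumed, to picture earlier detection.

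**Effect on the test.** Putting these readings into the rule above, the two-sided error is 3.6-4.5% in the first row and 3.9-4.7% in the second. It passes 5% only with early progression: 5.3% in the last cell of the third row and 5.9% in the fourth. At 13.89% it is 6.6%.

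**Check of the alternative.** In simulation (165 enrolled, 10% random loss, 40,000 trials per setting) the Kaplan-Meier estimate averages 12.5% at a true 12.5%. The planned ratio averages 13.3% with equal risk and all loss before biopsy 3, and 13.7% with all progression at biopsy 1 and all loss after it.

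**The case against.** The strongest reply is that the effect is small. With section 1.5.1 timing it is 0.2 to 0.7 points for loss after biopsy 1, against a 12.5-point target, and the error stays under 5%. That stands. A reader might infer that dropout alone could produce a positive trial; the figures do not support this.

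A second reply is that the plan already holds the remedy. One minus the product of (1 - rate) over the per-biopsy rates of 10.1.1 is essentially the product-limit estimate, and 10.5 names Kaplan-Meier. This stands in part: it would be wrong to say that the plan has no tool for missed biopsies. But the primary rate is tied explicitly to the completer ratio, no sensitivity analysis is attached to it, and the 24-month illustration in 10.5 words the per-biopsy rate differently.

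Third, the bias might cancel if the 12.5% was computed by the same rule. The documents do not say how it was computed. If it was, with section 1.5.1 timing and the same loss spread evenly over the last two intervals, the differences in the table's middle column would remain: 13.26 - 12.97 = 0.3 points (reverse order) to 13.70 - 12.97 = 0.7 (all at biopsy 1).

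Finally, the direction holds only for random dropout. Informative dropout could move the rate either way, so a reader should not conclude that the reported rate must be too high.

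**Conclusion.** The counting rule is biased as written, and nothing else in the plan repairs it. Under random 10% dropout the bias is never negative. It is 0 to 1.2 points at a true 12.5% and 0 to 2.0 at a true 25% if the 10% applies to men not yet progressed, or up to 1.4 and 2.8 if it applies to all enrolled. Section 10.4 does not state the base; 55 a year for three years less 10% is 165 × 0.9 = 148.5, close to the 150 used for power, which fits the enrolled base without settling it. No single value can be claimed, because the size depends on the timing of both loss and progression. The consequence is a modestly overstated primary estimate, not a large false-positive risk. The mechanism is certain; the size is not. It should be changed because the error favours the hypothesis and the change is cheap.

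**What to change.** In 10.1.1 and 10.5, state that the primary 24-month rate F is one minus the Kaplan-Meier estimate over the first three scheduled biopsies, with time counted in scheduled biopsies. Men without progression are censored at their last protocol biopsy up to the third. Treatment under criterion (v), as 10.1.1 now lists it, is an event in the biopsy interval in which it occurs; the opening of section 10 should be reconciled with this. Report F with the Greenwood log-log 95% interval already named.

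Keep the exact binomial comparison with 12.5%, using the effective sample size F(1 - F)/V in place of n, and that size times F in place of the event count, where V is the Greenwood variance. With no loss this is the planned test. State that this test decides if it and the interval disagree. Report the completer ratio as a sensitivity analysis. Compute the historical rate the same way if patient-level data allow; otherwise say that it was not possible.

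Cost: wording in 10.1.1, 10.4 and 10.5 and a little analysis time. The effective-sample-size step is new to the plan. In the same simulations its upper tail was 1.8-2.3% against a nominal 2.5%, and power at a true 25% with 165 enrolled and 10% loss was about 97-99%, so no more patients are needed. The log-log interval alone is less exact (upper tail roughly 3-4%), which is why it should not carry the test. Dropout is still assumed non-informative.
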